## 5.7 Study Termination

The study will be terminated 6 months after the last patient stops study treatment or up to 12 months after the last patient is enrolled, whichever is sooner.

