## 5.6 Second Course Phase (Retreatment Period)

Subjects who stop pembrolizumab with Stable Disease (SD) or better may be eligible for up to one year of additional pembrolizumab therapy if they progress after stopping study treatment. This retreatment is termed the Second Course Phase of this study and is only available if the study remains open and the subject meets the following conditions:

- **Either**
  - Stopped initial treatment with pembrolizumab after attaining an investigator-determined confirmed Complete Response (CR) according to RECIST 1.1, and
    - Was treated for at least 24 weeks with pembrolizumab before discontinuing therapy
    - Received at least two treatments with pembrolizumab beyond the date when the initial CR was declared
      - **OR**
  - Had SD, Partial Response (PR) or CR and stopped pembrolizumab treatment after 24 months of study therapy for reasons other than disease progression or intolerability

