#### **6.9.6 PERMANENT DISCONTINUATION OF STUDY TREATMENT**

Patients may discontinue study medication for the following reasons:

- Confirmed radiographic disease progression
- Unacceptable adverse experiences as described in Table 2
- Intercurrent illness that prevents further administration of treatment
- Investigator's decision to withdraw the subject
- The subject has a confirmed positive serum pregnancy test
- Non-compliance with trial treatment or procedure requirements
- Completed 24 months of uninterrupted treatment with pembrolizumab or 35 administrations of study medication, whichever is later
- Confirmed complete response (CR) and treated for at least 24 weeks with pembrolizumab and had at least two treatments with pembrolizumab beyond the date when the initial CR was declared.

A subject may be granted an exception to continue on treatment with confirmed radiographic progression if clinically stable or clinically improved.

24 months of study medication is calculated from the date of first dose. Subjects who stop pembrolizumab after 24 months may be eligible for up to one year of additional study treatment if they progress after stopping study treatment provided they meet the requirements detailed in Section 5.6.

Date of permanent discontinuation and the reason will be recorded.

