### 7.2 Adverse Event recording

AEs will be collected throughout the study, from the point of consent until the Safety Follow Up visit\*; they will be followed up according to local practice until the event has stabilised or resolved, or the follow-up visit, whichever is sooner. Serious Adverse Events (SAEs) will also be recorded throughout the study. See Appendix D for further details.

At the Safety Follow Up visit, any AEs of Grade > 1 which remain unresolved will be followed up by the Investigator until the resolution of the AE to Grade 0-1 or until the beginning of a new anti-neoplastic therapy, whichever occurs first, but without further recording in the eCRF.

\*SAEs, including death that occur within 90 days of the end of treatment or before initiation of a new anti-cancer treatment should also be followed and recorded.

Details to be collected in the eCRF for each AE will include:

- AE description
- Date of onset and date of resolution
- Severity
- Seriousness
- Relationship to study treatment

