## **7.8 Reporting of Pregnancy and Lactation**

Although pregnancy and lactation are not considered adverse events, it is the responsibility of investigators or their designees to report any pregnancy or lactation in a subject (spontaneously reported to them) that occurs during the trial.

Pregnancies and lactations that occur after the consent form is signed but before treatment allocation must be reported by the investigator if they cause the subject to be excluded from the trial, or are the result of a protocol-specified intervention, including but not limited to washout or discontinuation of usual therapy, diet, placebo treatment or a procedure.

Pregnancies and lactations that occur from the time of treatment allocation through 120 days following cessation of Sponsor's product, or 30 days following cessation of treatment if the subject initiates new anticancer therapy, whichever is earlier, must be reported by the investigator. All reported pregnancies must be followed to the completion/termination

CUPem	C/37/2017	Imperial College London	V7.0, 08.12.2021
-------	-----------	----------------------------	------------------

of the pregnancy. Pregnancy outcomes of spontaneous abortion, missed abortion, benign hydatidiform mole, blighted ovum, fetal death, intrauterine death, miscarriage and stillbirth must be reported as serious events (Important Medical Events). If the pregnancy continues to term, the outcome (health of infant) must also be reported.

Such events must be reported within 24 hours to the Sponsor, who will then report to MSD Global Safety within 2 days.

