#### **9.14 End of Trial**

The end of the trial is defined as the last data capture for the last patient on study; this will be 6 months after the last patient stops study treatment or up to 12 months after the last patient is entered whichever is sooner.

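### The 12-month closing limit can end data capture before a few patients' post-treatment safety windows have run

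*Protocol*

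**What the plan says.** Protocol 5.7 has two limbs. The first reads "The study will be terminated 6 months after the last patient stops study treatment". The second adds a cap that applies if it falls earlier: "or up to 12 months after the last patient is enrolled, whichever is sooner". Section 9.14 repeats the rule ("up to 12 months after the last patient is entered whichever is sooner") and fixes its meaning: "The end of the trial is defined as the last data capture for the last patient on study".

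Treatment can outlast the 12-month limb. Section 3.4 continues it until toxicity, progression or a decision to stop. Section 6.9.6 lists as one reason for stopping "Completed 24 months of uninterrupted treatment with pembrolizumab or 35 administrations of study medication, whichever is later". Under 5.6 some patients "may be eligible for up to one year of additional pembrolizumab therapy", provided the study is still open.

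After treatment the protocol sets these windows:

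- AE monitoring for 30 days (6.9.7).
- AE incidence to 8 weeks after the last dose, the secondary objective (Protocol 2.2; SAP 5.2 and 6.4).
- "SAEs, including death that occur within 90 days of the end of treatment", with allowance for an earlier start of new anti-cancer treatment (7.2; also 6.9.7).
- Events of clinical interest for 90 days, or 30 days if new anticancer therapy starts (7.10).
- Pregnancy and lactation "from the time of treatment allocation through 120 days following cessation", or 30 days if new anticancer therapy starts (7.8).

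**The concern.** The first limb waits for the last patient to stop and then adds 6 months, which is longer than any of the windows. Because the sooner limb governs, that protection goes whenever the last stop comes more than 6 months after the last enrolment. Patients who then stop close to the closing date, or have not stopped, have incomplete post-treatment safety data under the protocol's own definitions.

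This matters because Section 3.3.1 warns that immune-related events may appear several months after the last dose, and because post-treatment AE incidence is the secondary objective. The SAP does not impute missing data (6.8) and gives no rule for incomplete AE follow-up, so a truncated window would be counted as if it were complete. The better the drug works, the more patients are still on it at closure.

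**Working it through.** **Inputs.** Closing rule: Protocol 5.7 and 9.14. Windows of 30, 56, 90 and 120 days: Protocol 2.2, 6.9.7, 7.2, 7.8 and 7.10. Dosing every 21 days: Table 1. Median PFS of 2 months (null) and 4 months (alternative), and a sample size of 31 to 67: Protocol 8.2. Twenty patients first planned for Cohort 1: Protocol 8.2. One month is 30.44 days.

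**Treatment ceiling.** 35 × 21 = 735 days, and 735 / 30.44 = 24.1 months. The plan's 24 months and 35 administrations therefore agree. Dosed every 21 days from day 0, the last-enrolled patient has had at most 17 + 1 = 18 of 35 doses by day 365.

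**When each limb governs.** Six months is 183 days, more than 120, so under the first limb every window is complete. If the last stop is more than 6 months after last enrolment, closure falls no later than day 365 after last enrolment. A window of w days is then complete only if the patient stops by day 365 − w.

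| Window | Cut if treatment stops later than (after last enrolment) |
|---|---|
| 120-day pregnancy | day 245 (8.1 months) |
| 90-day SAE and events of clinical interest | day 275 (9.0 months) |
| 8-week AE | day 309 (10.2 months) |
| 30-day AE | day 335 (11.0 months) |

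A patient still on drug at closure has no post-treatment window at all.

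**How many patients.** The documents give no distribution of treatment duration, so I assume it is exponential and equal to PFS with median m. I also assume even accrual over the final 12 months and closure at the full 12 months. The number accrued in that period is taken as 31 − 20 = 11 up to 67 − 20 = 47. With w in months, the chance that a patient's window is cut is

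P(w) = 2^(−(12 − w)/m) × A, where A = [m / (12 ln 2)] × [1 − 2^(−12/m)].

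A is 0.2367 for m = 2 and 0.4208 for m = 4. For the 90-day window at m = 4, P = 0.2087 × 0.4208 = 0.0878, which gives 0.97 of 11 and 4.13 of 47 patients.

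| Expected patients (11 to 47 accrued) | m = 2 months | m = 4 months |
|---|---|---|
| Still on drug at closure | 0.04–0.17 | 0.58–2.47 |
| 30-day window cut | 0.06–0.24 | 0.69–2.93 |
| 8-week window cut | 0.08–0.33 | 0.80–3.40 |
| 90-day window cut | 0.11–0.48 | 0.97–4.13 |
| 120-day window cut | 0.16–0.68 | 1.15–4.90 |

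Each row includes the patients in the rows above it.

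**Does anything restore the windows?** Protocol 5.7.1 passes patients to local standard of care. Section 7.4.2 asks for drug-related information after a patient has completed the study, but only if the investigator becomes aware of it. Section 11.2 requires end-of-treatment assessments on early discontinuation of the study, not the later windows. No section keeps data capture open for these patients.

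**The case against.** The strongest reply is that the loss is conditional and small. It needs someone to stop more than about 8 months after last enrolment. The 12 months is a ceiling. The SAE, clinical-interest and pregnancy windows shorten by their own terms if new anti-cancer therapy starts. Section 5.4 makes the 30-day visit mandatory, and 7.4.2 leaves a passive reporting route. The upper count of 47 is also generous: Protocol 1.3.1 dates the decision to lift the Cohort 1 cap to January 2021, so some of those patients may have enrolled before the final 12 months. All of this stands and limits the size, but none of it collects the data that the windows require.

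Three stronger readings are tempting, and the documents do not support them.

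- **The affected patients are the trial's only source of late-toxicity data.** Cohort 1 already had a documented response in May 2020. If the last patient enters on 31 December 2022 and closure is on 31 December 2023, anyone enrolled by about 2 September 2021 has room for 24 months plus 120 days. Nor need every affected patient have long exposure: under 5.6 a complete responder may stop after 24 weeks and restart shortly before closure.
- **The 24-month rule and the second course flatly contradict closure.** Section 6.9.6 sets a ceiling, not a promised duration. Sections 5.6 and 6.9.9 both make retreatment conditional on the study being open.
- **AE incidence is shown to be biased.** The direction is plausible, since missed events can only lower the count, but no size has been shown. On-treatment events are captured, and any-AE incidence would change for few patients. Routine AE recording in 7.2 also stops at the safety visit at about 30 days, so the 8-week objective is not fully supported even without early closure.

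**Conclusion.** The point holds as a conflict between the closing rule (5.7, 9.14) and the protocol's own post-treatment windows (2.2, 6.9.7, 7.2, 7.8, 7.10). It affects only patients on drug, or within about 120 days of stopping, when the 12-month limit applies. For the SAE window that is about 0.1 to 0.5 patients at a 2-month median PFS and about 1 to 4 at a 4-month median. These counts rest on exponential treatment time equal to PFS, 11 to 47 patients accrued evenly over the final 12 months, closure at the full 12 months, and no allowance for second courses or for windows shortened by new therapy. The day limits in the working rest on none of the accrual or duration assumptions. It is worth correcting because a stated rule, rather than a missing detail, removes safety follow-up that the protocol requires. It does not undermine the safety analysis as a whole.

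**What to change.** Reconcile 5.7 and 9.14 with 2.2, 6.9.7, 7.2, 7.8 and 7.10. Add that safety data capture, but not efficacy visits or imaging, stays open after the closing date until each patient's post-treatment windows have run from the last in-trial dose. The windows should be those defined in Sections 2.2 and 7, including their shortening when new anti-cancer therapy starts. Settle the 8-week objective against the 30-day recording period in 7.2 at the same time.

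The sponsor should also state how 5.7 and 5.7.1 apply to a patient still on drug at closure, and reconcile them with 5.6 and 6.9.6. No dosing or stopping rule is proposed here.

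The cost is a short amendment and up to about 4 months (120 / 30.44 = 3.9) of extra safety data capture after the last in-trial dose, for a handful of patients. The reference to safety capture only, and a clear statement of what counts as the last in-trial dose, both matter. A sentence that simply kept the whole trial open until every window had run could hold it to about month 28 (24 + 3.9 = 27.9) for a last-enrolled patient who reached the 24-month ceiling, and longer with a second course.

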### 5.7.1 Treatment after Study Termination

Following participation in the study, patient management will be according to local standard of care.

### 5.7.2 Clinical Criteria for Early Trial Termination

Early trial termination will be the result of the criteria specified below:

1. Quality or quantity of data recording is inaccurate or incomplete
2. Poor adherence to protocol and regulatory requirements
3. Incidence or severity of adverse drug reaction in this or other studies indicates a potential health hazard to subjects
4. Plans to modify or discontinue the development of the study drug.

In the event of MSD decision to no longer supply study drug, ample notification will be provided so that appropriate adjustments to subject treatment can be made.

## 5.8 Study Schedules during Treatment

Table 3 summarizes the trial procedures to be performed at each visit. Individual trial procedures are described in detail below. Treatment is divided into cycles of 21 days, with visits and assessments specified according to the relevant cycle.

Unless otherwise indicated, scheduled assessments may take place within  $\pm 3$  days of the specified visit. Assessment days are relative to the start of study treatment i.e. Cycle 1 Day 1.

If a patient has a treatment break, please contact the Clinical Trials Section (CTS) for advice regarding the timing of research blood assessments. All other assessments, including laboratory safety assessments, vital signs and radiological imaging should continue to be performed.

CUPem	C/37/2017	Imperial College London	V7.0; 08.12.2021
-------	-----------	----------------------------	------------------

Furthermore, additional evaluations/testing may be deemed necessary by the Sponsor and/or MSD for reasons related to subject safety. In some cases, such evaluation/testing may be potentially sensitive in nature (e.g., HIV, Hepatitis C, etc.), and thus local regulations may require that additional informed consent be obtained from the subject. In these cases, such evaluations/testing will be performed in accordance with those regulations.

**During the COVID-19 pandemic, patients whom are under ongoing treatment can be offered longer intervals of 1 to 2 weeks between treatment to avoid peak COVID-19 capacity issues.**

CUPem	C/37/2017	Imperial College London	V7.0; 08.12.2021
-------	-----------	----------------------------	------------------

**Table 3: Table of Assessments**

Trial Period:	Screening Phase	Treatment Cycles								End of Treatment	Post-Treatment		
Treatment Cycle/Title:	Study Screening	1	2	3	4	To be repeated beyond 8 cycles				Discon	Safety Follow-up	Follow Up Visits	Survival Follow-Up
						5	6	7	8				
Scheduling Window (Days):	-28 to -1		± 3	± 3	± 3	± 3	± 3	± 3	± 3	At time of Discon	30 days post discon	Every 8 weeks post discon	Every 12 weeks
Administrative Procedures													
Pre-screening Visit													
Informed Consent	X												
Inclusion/Exclusion Criteria	X												
Demographics and Medical History	X												
Prior and Concomitant Medication Review	X	X	X	X	X	X	X	X	X	X	X		
Trial Treatment Administration		X	X	X	X	X	X	X	X				
Trial Treatment Compliance		X	X	X	X	X	X	X	X				
Quality of Life Questionnaire (EORTC QLQ-C30)	X					X				X			
Post-study anticancer therapy status											X	X	X
Survival Status		X	X	X	X	X	X	X	X	X	X	X	X
Clinical Procedures/Assessments													
Review Adverse Events	X	X	X	X	X	X	X	X	X	X	X		
Full Physical Examination	X a	X			X				X	X	X		
Directed Physical Examination	X a	X	X	X	X	X	X	X	X	X	X	X	
Vital Signs and Weight	X a	X	X	X	X	X	X	X	X	X	X	X	
ECOG Performance Status	X a	X	X	X	X	X	X	X	X	X	X	X	
Laboratory Procedures/Assessments: analysis performed by LOCAL laboratory													
Pregnancy Test –Serum β-HCG	X b		X c		X c		X c		X c				
PT/INR and aPTT	X d	X e	X e	X e	X e	X e	X e	X e	X e	X	X	X	
CBC with Differential	X d	X e	X e	X e	X e	X e	X e	X e	X e	X	X	X	

CUPem	C/37/2017	Imperial College London	V7.0, 08.12.2021
-------	-----------	----------------------------	------------------

Trial Period:	Screening Phase	Treatment Cycles								End of Treatment	Post-Treatment		
Treatment Cycle/Title:	Study Screening	1	2	3	4	To be repeated beyond 8 cycles				Discon	Safety Follow-up	Follow Up Visits	Survival Follow-Up
						5	6	7	8				
Scheduling Window (Days):	-28 to -1		± 3	± 3	± 3	± 3	± 3	± 3	± 3	At time of Discon	30 days post discon	Every 8 weeks post discon	Every 12 weeks
Comprehensive Serum Chemistry Panel including full or directed tumor marker panel (+/- NET serum markers)	X d	x e	X e	X e	X e	X e	X e	X e	X e	X	X		
Urinalysis	X d	X e	X e	X e	X e	X e	X e	X e	X e	X	X		
T3, FT4 and TSH	X d	x e	X e	X e	X e	X e	X e	X e	X e	X	X	X	
Efficacy Measurements													
Tumor Imaging	X f					X g			X	X (if not done within 12 weeks prior)		X	
Tumor Biopsies/Archival Tissue Collection/Correlative Studies Blood													
Archival or Newly Obtained Tissue Collection	X h												
Correlative Studies Blood & Urine Collection	X		X		X		X		X	X	X		

CUPem	C/37/2017	Imperial College London	V7.0, 08.12.2021
-------	-----------	----------------------------	------------------

Trial Period:	Screening Phase	Treatment Cycles								End of Treatment	Post-Treatment		
Treatment Cycle/Title:	Study Screening	1	2	3	4	To be repeated beyond 8 cycles				Discon	Safety Follow-up	Follow Up Visits	Survival Follow-Up
Scheduling Window (Days):	-28 to -1		± 3	± 3	± 3	± 3	± 3	± 3	± 3	At time of Discon	30 days post discon	Every 8 weeks post discon	Every 12 weeks
a In circumstances where screening assessments are conducted within 3 days prior to treatment initiation these can be used to cover both screening and C1D1.													
b Mandatory negative blood serum pregnancy test at screening for patients of childbearing potential.													
c In patients of childbearing potential: 
 
• Mandatory negative serum pregnancy test within 72 hours prior to receiving study treatment
 
• Mandatory negative urine pregnancy test result available prior to receiving study treatment
 
													
d Lab tests (blood samples for haematology, clinical chemistry and urinalysis) for screening should be performed within 10 days prior to the first dose of treatment. In circumstances where blood samples for haematology and clinical chemistry and urinalysis fulfils both the timeline of day -10 to 0 and 72 hours prior to C1D1 dosing these can be used for both screening and C1D1.													
e On dosing days for all cycles, samples must be taken pre-dose (up to 72 hours prior to dosing).													
f Baseline assessment should be performed no more than 28 days before the start of study treatment and ideally as close as possible to the start of the study treatment.													
g Subsequent tumour assessments will be conducted every 12 weeks, with window for each assessment is ± 7 days.													
h Tumour blocks / slides should be made available within 60 days of patient enrolment.													

CUPem	C/37/2017	Imperial College London	V7.0, 08.12.2021
-------	-----------	----------------------------	------------------

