### 4.2 Inclusion Criteria

Patients who meet all of the following inclusion criteria will be considered eligible for this study:

1. Be willing and able to provide written informed consent/assent for the trial.
2. Be  $\geq 18$  years of age on day of signing informed consent.
3. Have measurable disease based on RECIST 1.1.
4. Be willing to provide consent for archival tumour (in the form of formalin fixed paraffin embedded (FFPE) block) or fresh tumour material (if judged technically feasible by radiologist) is mandatory for diagnosis and biomarker analysis.
5. Have a performance status of 0-2 on the ECOG Performance Scale.
6. Have had at least one prior line / regimen of chemotherapy appropriate for CUP (at least 2 cycles). Either did not have a RECIST response to first-line chemotherapy or progressing after an initial response, or are treatment intolerant to first-line chemotherapy due to unacceptable toxicity.
7. Adequate organ and bone marrow function (all screening tests should be performed within 10 days of treatment initiation):
  - a. Absolute neutrophil count (ANC)  $\geq 1.5 \times 10^9/L$
  - b. Platelets  $\geq 100 \times 10^9/L$
  - c. Haemoglobin  $\geq 9$  g/dL ( $\geq 90$  g/L) without transfusion or EPO dependency (within 7 days of assessment)
  - d. Serum creatinine  $\leq 1.5 \times$  Upper Limit of Normal (ULN) or Creatinine clearance\*  $\geq 60$  mL/min for patients with creatinine levels  $> 1.5 \times$  ULN  
\* Creatinine clearance should be calculated per institutional standard
  - e. Serum total bilirubin  $\leq 1.5 \times$  ULN or direct bilirubin  $\leq$  ULN for patients with total bilirubin levels  $> 1.5$  ULN
  - f. Aspartate aminotransferase [AST]  $\leq 2.5 \times$  ULN ( $< 5 \times$  ULN if liver metastases are present)
  - g. Alanine aminotransferase [ALT]  $\leq 2.5 \times$  ULN ( $< 5 \times$  ULN if liver metastases are present)
  - h. Albumin  $\geq 2.5$ g/dL
  - i. International Normalized Ratio (INR) or Prothrombin Time (PT)  $\leq 1.5 \times$  ULN (unless subject is receiving anticoagulant therapy as long as PT or PTT is within therapeutic range of intended use of anticoagulants)
  - j. Activated Partial Thromboplastin Time (APTT)  $\leq 1.5 \times$  ULN (unless subject is receiving anticoagulant therapy as long as PT or PTT is within therapeutic range of intended use of anticoagulants).

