#### 4.3 Exclusion Criteria

Patients who meet any of the following exclusion criteria will **not** be eligible for this study:

- Is currently participating and receiving study therapy or has participated in a study of an investigational agent and received study therapy or used an investigational device within 4 weeks of the first dose of treatment.
- Has a diagnosis of immunodeficiency or is receiving systemic steroid therapy or any other form of immunosuppressive therapy within 7 days prior to the first dose of trial treatment.
- Has a known history of active TB (Bacillus Tuberculosis).
- Hypersensitivity to pembrolizumab or any of its excipients.
- Has had a prior anti-cancer monoclonal antibody (mAb) within 4 weeks prior to study Day 1 or who has not recovered (i.e.,  $\leq$  Grade 1 or at baseline) from adverse events due to agents administered more than 4 weeks earlier.
- Has had prior chemotherapy, targeted small molecule therapy, or radiation therapy within 2 weeks prior to study Day 1 or have not recovered (i.e.,  $\leq$  Grade 1 or at baseline) from adverse events due to a previously administered agent.
  - Note: Subjects with  $\leq$  Grade 2 neuropathy are an exception to this criterion and may qualify for the study.
  - Note: If subject received major surgery, they must have recovered adequately from the toxicity and/or complications from the intervention prior to starting therapy.
- Has a known additional malignancy that is progressing or requires active treatment. Exceptions include basal cell carcinoma of the skin or squamous cell carcinoma of the skin that has undergone potentially curative therapy or in situ cervical cancer.
- Has known active central nervous system (CNS) metastases and/or carcinomatous meningitis. Subjects with previously treated brain metastases may participate provided they are stable (without evidence of progression by imaging for at least four weeks prior to the first dose of trial treatment and any neurologic symptoms have returned to baseline), have no evidence of new or enlarging brain metastases, and are not using steroids for at least 7 days prior to trial treatment. This exception does not include carcinomatous meningitis which is excluded regardless of clinical stability.

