### **5.2 Study Screening Assessments**

Written informed consent will be obtained before the patient undergoes any study specific procedures. Consent must be documented by the subject's dated signature or by the subject's legally acceptable representative's dated signature on a consent form along with the dated signature of the person conducting the consent discussion.

A copy of the signed and dated consent form should be given to the subject before participation in the trial.

Each patient will undergo screening during the 28 days prior to admission to confirm eligibility, as per Table 3. Tumour assessments and other clinical data obtained as standard of care prior to consent may be used for the study provided they comply with the protocol specified timelines.

Once consent has been obtained the patient should be added to the InForm Electronic Case Report Form (eCRF), where a unique Screening ID will be allocated, which should be used in all correspondence during the screening period.

A complete record of all patients who enter screening for the study, and also those who go on to be enrolled, must be maintained at each site. The local investigator is responsible for ensuring that this record includes the allocated trial ID as well as the patient identifiable data including name, hospital number and date of birth.

Eligible patients who take part in the study must meet all of the listed inclusion criteria and none of the exclusion criteria.

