#### **5.9.14 Quality of Life**

The QOL instrument, EORTC QLQ-C30 version 3 will be administered as specified in Table 3 and must be completed before other assessments are performed or study drug is administered.

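### The only pre-treatment QLQ-C30 may be up to 28 days old at the first dose, so off-drug change of either sign enters the uncontrolled before-after QoL comparison

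*Protocol*

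**What the plan says.** Protocol Table 3 and SAP Table 2 agree: the row "Quality of Life Questionnaire (EORTC QLQ-C30" is marked at screening, Cycle 5 and discontinuation, and the Cycle 1 cell is blank. Screening spans Day -28 to Day -1; Protocol 5.2 puts it as "Each patient will undergo screening during the 28 days prior to admission to confirm eligibility". On timing, Protocol 5.9.14 adds only that the form "must be completed before other assessments are performed or study drug is administered".

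Other baseline measures are kept closer to dosing. Footnote a of Table 3, attached to physical examinations, vital signs and ECOG status, reads: "In circumstances where screening assessments are conducted within 3 days prior to treatment initiation these can be used to cover both screening and C1D1". Outside that window they are repeated at Cycle 1. Screening laboratory tests fall within 10 days of the first dose, and dosing-day samples within 72 hours. The QoL row carries no footnote.

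Protocol 4.3 excludes a patient who "Has had prior chemotherapy, targeted small molecule therapy, or radiation therapy within 2 weeks prior to study Day 1 or have not recovered" from earlier adverse events. Protocol 4.2, criterion 6, gives as one of its entry routes patients who "are treatment intolerant to first-line chemotherapy due to unacceptable toxicity". Protocol 6.7.2 bars chemotherapy and radiotherapy during the screening and treatment phases.

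The primary hypothesis in both documents includes rapid QoL improvement due to treatment. SAP 5.1 lists QoL under the primary efficacy endpoint. SAP 6.3 compares scores between visits by repeated-measures ANOVA or Friedman's test, with no term for the gap from form to first dose or for time since chemotherapy.

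**The concern.** There is no control arm, so the baseline form is the only reference for a claim that QoL improved on pembrolizumab. If that form is several weeks old at the first dose, part of the reported change happened off drug.

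Two processes could drive that part. A patient who has just finished a poorly tolerated regimen may recover before dosing, which would look like benefit. A patient with fast-progressing disease may worsen before dosing, which would hide benefit. The planned analysis cannot separate either from a drug effect. What is at stake is the interpretation of the QoL result. PFS, OS, disease control and safety are not affected.

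**Working it through.** The plan states no figure on this point, so there is nothing to reproduce. The check is calendar arithmetic on the schedule.

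**Inputs**
- Cycle length 21 days (Protocol 5.8), so Cycle 5 Day 1 is 4 × 21 = 84 days after C1D1, which matches the 3-month form.
- Baseline form g days before C1D1, with g from 1 to 28 (Table 3).
- Washout of 14 days counted back from Day 1 (Protocol 4.3).
- No chemotherapy or radiotherapy during screening (Protocol 6.7.2).

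**Step 1. Untreated share of the baseline-to-Cycle 5 interval**

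Interval = g + 84 days; untreated share = g / (g + 84).

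| Form on | Interval (days) | Untreated share |
|---|---|---|
| Day -1 | 85 | 1/85 = 1% |
| Day -3 | 87 | 3/87 = 3% |
| Day -14 | 98 | 14/98 = 14% |
| Day -28 | 112 | 28/112 = 25% |

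With the ±3-day window at Cycle 5, the interval can run from 82 to 115 days.

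**Step 2. How soon after chemotherapy the form can be completed**

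The last cycle must be at least 14 days before Day 1 and must also precede screening. The shortest time from last cycle to form is therefore max(0, 14 − g) days.
- Form on Day -14 or earlier: it can follow the last cycle almost at once.
- Form on Day -3: at least 14 − 3 = 11 days after.
- Form at C1D1: at least 14 days after.

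A Day -28 form means that the last cycle was before Day -28. That patient has up to 28 days of untreated recovery or decline between form and first dose. Nothing ties the washout or the recovery condition to the date of the form.

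**Step 3. Where the change goes**

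Reported change = (Cycle 5 score − Day 1 score) + (Day 1 score − screening score).

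The second bracket is entirely off drug. With no Day 1 form it cannot be estimated or removed. It enters the baseline-to-discontinuation contrast in the same way, but not the Cycle 5-to-discontinuation contrast.

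**Step 4. Can this be turned into an error rate?**

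Only by assumption, because the documents give no QoL standard deviation and no pre-dose drift. For a paired two-sided 5% z-test, no drug effect, and a mean drift of d standard deviations of the change score, the rejection rate is Φ(d√n − 1.96) + Φ(−d√n − 1.96).

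| Assumed d | n = 31 | n = 67 |
|---|---|---|
| 0 | 5% | 5% |
| 0.1 | 9% | 13% |
| 0.3 | 39% | 69% |
| 0.5 | 80% | 98% |

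Here d is the net drift averaged over the whole cohort. If one third of patients shift by 0.3 and the rest not at all, d is 0.3/3 = 0.1. If some recover while others decline, d may be near zero. The range shows how much the answer depends on an unknown; it is not an estimate for this trial.

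**The case against.** A reader might infer that recovery from toxic chemotherapy will be scored as improvement on pembrolizumab. The documents do not support that as a prediction. Patients also enter because their disease is progressing or did not respond, and pre-dose worsening would bias the change the other way. Criterion 6 concerns intolerance of first-line chemotherapy. It does not say that this was recent, and later lines may have followed.

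A reader might also infer from the 14-day washout that the form can be completed before or during the last chemotherapy. Protocol 6.7.2 rules that out, since the form is a screening procedure.

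Nor is 28 days the expected gap. Protocol 3.2 asks for treatment to begin on the day screening and consent are complete, or as soon as possible around allocation. That makes 28 days the outer limit, although it does not restrict when within screening the form is completed.

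It is tempting to set 28 days against the 2-month null median PFS, or to quote one of the higher rejection rates above. The first ratio says nothing about QoL. The second rests on a cohort-wide drift with no support in the documents, and on a simpler test than the one planned, which covers three visits with adjustment for multiple testing.

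Finally, a 28-day baseline window is ordinary, and baseline imaging has the same limit. QoL has no sample-size basis or decision rule, and the protocol calls the trial hypothesis generating. All of this stands and limits the weight of the point. It does not remove it: footnote f asks for imaging as near the start of treatment as possible, footnote a applies a 3-day rule to other assessments, and the QoL form has neither.

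**Conclusion.** The point holds as a timing weakness in the QoL comparison. The only baseline QLQ-C30 may precede dosing by up to 28 days, and off-drug change of either sign over that time is counted in the change from baseline. At the outer limit, 25% of the baseline-to-Cycle 5 interval is untreated; for a Day -1 form it is 1%. The size and sign of the resulting bias are unknown, because the documents give neither the gap from form to dose nor the share of patients with recent chemotherapy.

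The conclusion rests on two readings: that the blank Cycle 1 cell means no form is taken then, and that footnote a does not extend to the QoL row, where it is not marked. Correcting the timing is a cheap improvement. It does not make the QoL result a controlled one: recovery that continues after Day 1 stays confounded with treatment in a single-arm trial, wherever the baseline form is placed.

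**What to change.** **Patients still to be enrolled.** Schedule the baseline QLQ-C30 at C1D1 before dosing, or accept the screening form only if completed within 3 days before C1D1, as footnote a already does for other assessments. Define baseline in the SAP as that form.

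**Patients already enrolled.** Report the distribution of the gap from form to first dose and of time since last chemotherapy. Add a sensitivity analysis limited to forms completed close to C1D1, with the cut-off fixed before the scores are examined. The number of such forms is not known from the documents and may be small.

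**Reporting.** State that the change removes pre-dose drift only, and that continuing recovery after Day 1 cannot be separated from a treatment effect without a control.

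**Cost.** No extra form or visit. Patients never dosed would have no QoL form, but they are already outside the QoL analysis, which uses per-protocol patients with at least 2 cycles. The real costs are a protocol amendment, a matching SAP edit, and mixed baseline timing within one small cohort, since Cohort 1 had already enrolled patients before it was reopened. The sensitivity analysis makes that mixture visible but does not remove it.
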